#### **4.4.2 Physical Examinations**

Physical examination findings will be listed for each patient.

#### **4.4.3 Vital Signs**

Systolic blood pressure, diastolic blood pressure, heart rate, respiratory rate and temperature are summarized using descriptive statistics for each visit. Both actual values and changes from baseline are summarized.

#### **4.4.4 ECG assessments**

The core laboratory's interpretation of the ECGs are summarized as "shift" from baseline to "worst" overall interpretation recorded after baseline where the order of severity of the interpretations from best to worst are "Normal", "Abnormal, NCS" and "Abnormal, CS". Separate summaries are used for post baseline data collected during double-blind and during open-label. If applicable, follow-up visits are included in the post-baseline data dependent upon entry into open-label (ie included in double-blind assessment if a patient did not enter open-label and in open-label assessment if they did).

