Protocol Amendment 1, Version 2.0, dated 06FEB2018 added a 6-month open-label extension to allow subjects to receive ATI-50002 Topical Solution, 0.46%. In addition, to assist with enrollment and to facilitate enrollment of subjects less than 60 years of age, the amendment specified that after the first 6 subjects were enrolled in the study, the blood PK samples were no longer collected. Administrative Letters 1 through 5 were incorporated into Protocol Amendment 1. Administrative Letter #1 (dated October 2, 2017) outlined the change from a single center to a multicenter study, clarified that M689 would not be measured and that the method for the detection of ATI-50002 in the scalp was a qualified method. Administrative Letter #2 (dated December 19, 2017) added superficial tape stripping of the scalp biopsy site for pharmacokinetic analysis to remove any residual study medication in the upper layers of the stratum corneum prior to biopsy. Administrative Letter #3 (dated January 22, 2018) allowed for a decrease in the volume of study medication applied from 4 mL to 1.5 mL to 4 mL, and Administrative Letter #4 (dated January 29, 2018) updated the address for Aclaris Therapeutics, Inc. Administrative Letter #5 (dated 03AUG2018) clarified the treatment duration of the Open Label Extension (OLE) portion of the study for subjects with a gap between Visit 7 and entry into the OLE due to an administrative delay.

AMENDMENT RATIONALE:

The primary purpose of Amendment 2, Version 3.0 dated 14AUG2018 is to increase the duration of the open-label extension (OLE) to 12 months.

Protocol Version	Date	Section	Revision
Version 1.0	26JUL2017	NA	NA
Version 2.0	06FEB2018	Title page	Replaced single center with multicenter in the title and added 6-Month Long-term open label Extension
		Protocol Approval Signature Page	
		Investigator Signature Page	
		Synopsis	
		Title page	Removed [name]
		Title page	Updated the Medical Monitor to: [name], RAC
		Section 10.2.2, Procedure for Reporting Adverse Events	
		Synopsis, Number of Study Sites	Updated site number to two.
		Section 6.1, Number of Subjects	
		Synopsis, Study Design, Endpoints, Statistical Methods	Concentrations of M689 in the blood will not be measured.
		Section 7.1 Overall Study Design	
		Section 9.3.2 Blood Samples	
		Section 12.4 Pharmacokinetic Analysis	

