
16. Participation in an investigational drug or device trial in which administration of an investigational study drug or device occurred within 30 days or 5 half-lives (whichever is longer) of Screening (Visit 1). Subjects who have participated in a study of an investigational drug, device or biologic agent for alopecia areata (AA, AU or AT) within 1 year of screening will be eligible to participate only with individual permission from the Medical Monitor.
 
17. Sensitivity to any of the ingredients in the study medications.
 
18. History of or current alcohol or drug abuse within 2 years of assessment for study enrollment.
 
19. Screening ECG findings of:
 
 • QTcF >450msec for males or >470msec for females (use of the ECG algorithm is acceptable for this purpose) • Heart rate < 45 or > 100 beats/minutes (inclusive) • Rhythm disturbance other than sinus arrhythmia or ectopic supraventricular rhythm (ectopic atrial rhythm) • Conduction disturbance including PR >240msec, pre-excitation (delta wave and PR <120msec), second degree or higher AV block • Acute or chronic signs of ischemia • Left Bundle Branch Block • Prior myocardial infarction 		

Duration of Treatment
 
Double-blind Treatment
 
Screening period up to 30 days.
 
Double-blind treatment period is 29 days (maximum of 28 days of study medication application).
 
Post-treatment Visit 16 is up to 33 days (30 +3 days) following Day 29 for subjects not continuing into the open-label extension.
 
Total study participation for subjects from Baseline (Visit 2) through Post-treatment Visit 16(Day 59 + 3 days) is up to 62 days (29 + 33).
 
Double-Blind + Open-Label Extension
 
The duration of the total study participation from Baseline (Visit 2) to Week 56 (Visit 16) is anticipated to be a maximum of 400 days (393 + 7 days).
 
The duration of the open-label extension (OLE) should be based on the date of the visit that the subject initiated OLE treatment rather than the days from Baseline (Visit 2). For subjects who entered the open-label extension and had a gap between Visit 7 and entry into the open-label extension due to an administrative delay total study participation may be longer than 400 days.
		

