7.5. Duration of the Study

The anticipated time for study enrollment is 3 to 6 months. The duration of the screening period is up to 30 days. The expected double-blind treatment period for each subject is 29 days (maximum of 28 days of study medication application). The post-treatment follow-up period is up to 33 days (30 + 3-day window). The maximum total study duration for the double-blind period from the subject's first visit (Visit 1) through the subject's last visit (Visit 8) is 92 days. On Day 1 (Visit 2) and Day 28 (Visit 6), subjects are required to be confined at the investigational center until all study procedures are completed. The confinement period may last approximately 10 hours. The duration of the total study participation from Baseline (Visit 2) to the open-label post-treatment follow up visit, Week 56 (Visit 16) is anticipated to be a maximum of 400 days. The duration of the open-label extension (OLE) should be based on the date of the visit that the subject initiated OLE treatment rather than the days from Baseline (Visit 2). For subjects who entered the open-label extension and had a gap between Visit 7 and entry into the open-label extension due to an administrative delay total study participation may be longer than 400 days.

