## 4. STATISTICAL METHODS

In general summaries will be presented according to double-blind treatment group and additionally for the subset of patients entering open-label. Other than baseline data (ie data collected prior to the first application of double-blind medication), the data summarized corresponds to the period of collection (ie during double-blind or during open-label). For those entering open-label, the open label period begins at the application of open-label medication. Additional details are provided in the data handling and programming specifications document. No imputation of missing data was performed other than completely or partially missing dates as described in the Data Handling and Programming Specifications document.

All Data listings are sorted by double-blind treatment group and patient ID.

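### SAP 4.4.4 allocates follow-up ECGs by whether the patient ever entered open-label, with no date condition, so any follow-up ECG taken before open-label drug would be counted as open-label

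*SAP*

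**What the plan says.** SAP 4.4.4 summarises the core laboratory's ECG interpretation as a shift from baseline to the worst reading after baseline. It first splits the data by period: "Separate summaries are used for post baseline data collected during double-blind and during open-label". It then adds a rule for follow-up visits: "If applicable, follow-up visits are included in the post-baseline data dependent upon entry into open-label", explained in a parenthesis as "included in double-blind assessment if a patient did not enter open-label and in open-label assessment if they did".

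SAP Section 4 gives the general rule. Apart from baseline, "the data summarized corresponds to the period of collection (ie during double-blind or during open-label"), and "For those entering open-label, the open label period begins at the application of open-label medication".

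The protocol provides for subjects who did not go straight from Visit 7 into the extension. Section 7.5 refers to subjects who "had a gap between Visit 7 and entry into the open-label extension due to an administrative delay", and footnote 17 of the schedule allows entry after Day 29 through an unscheduled visit, with no maximum gap stated.

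**The concern.** The 4.4.4 parenthesis turns on a fact about the patient (did they ever enter open-label?) rather than a fact about the ECG (when was it taken?). The two agree when an entrant's only follow-up visit comes after open-label treatment. They disagree when a subject had a follow-up visit after the double-blind period and started open-label drug afterwards.

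In that case three things go wrong:

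- An off-drug ECG counts as open-label ATI-50002 data. If the subject was randomised to vehicle, the reading comes from someone not yet exposed to ATI-50002.
- The same ECG is missing from the double-blind table, the only ECG summary with a vehicle group.
- The ECG and adverse event tables can disagree. Protocol 9.5.5 has clinically significant post-treatment ECG abnormalities reported as adverse events, and SAP 4.4.1 classifies those by onset date. An event in the gap is never open-label under 4.4.1, but the matching ECG would be under 4.4.4.

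Because the table keeps the worst reading, one ECG can set a subject's category.

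**Working it through.** The plan has no figure to reproduce here, so the check sets the two rules against possible subject timelines.

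**Inputs**

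- Post-baseline ECGs in the schedule (Protocol 7.3, SAP Section 3): Visit 5 (Day 15), Visit 7 (Day 29), Visit 9 (OLE 56), Visit 13 (OLE 168) and Visit 16. Visit 16 is Day 59 for subjects not continuing, and OLE 364 for those who do (29 + 364 = Day 393).
- Visit 7 sits in the double-blind block, so the follow-up rule does not reach it.
- The late-entry unscheduled visit covers consent, instructions and dispensing, plus baseline eyebrow scores (footnotes 17 and 18). No ECG is listed.

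**Rules**

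- Rule A, 4.4.4 read literally: a follow-up ECG is open-label if the subject ever entered, otherwise double-blind. Other ECGs go by date.
- Rule B, Section 4: an ECG is open-label only from the first open-label application; before that it is double-blind.

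**Timelines** (gap lengths in 3 and 4, and the Day 59 ECG in 4, are assumptions)

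1. Never enters: Days 15, 29 and 59 are double-blind under both rules. Differences: 0.
2. Enters at Visit 7: Days 15 and 29 are double-blind; Days 85, 197 and 393 are open-label. Differences: 0.
3. 20-day gap, open-label from 29 + 20 = Day 49, current schedule: Days 15 and 29 are double-blind; 49 + 56 = 105, 49 + 168 = 217 and 49 + 364 = 413 are open-label. Differences: 0.
4. 90-day gap, open-label from 29 + 90 = Day 119, with a follow-up ECG on Day 59: Days 175, 287 and 483 are open-label under both. Day 59 is open-label under A and double-blind under B. Differences: 1.

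Only timeline 4 triggers the conflict.

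**Could timeline 4 occur?**

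- The extension was added by Amendment 1, dated 06FEB2018. Day 59 is 58 days after Day 1, and 06FEB2018 minus 58 days is 10DEC2017. Anyone with Day 1 on or before that date reached Day 59 no later than the amendment date. Their Day 29 was 07JAN2018 or earlier, so if they later entered, the gap was at least 30 days.
- Protocol 7.5 still describes a double-blind path of 30 + 29 + 33 = 92 days ending at Visit 8, which suggests an earlier schedule with its own post-treatment visit.
- No enrolment dates are given, nor the ECG content of that earlier visit.

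**Adverse event rule for comparison** (SAP 4.4.1). With the last double-blind application on Day 28, Day 59 is 59 − 28 = 31 days later. Being more than 30 days, an event then is post-therapy; on Day 58 (30 days) it would be double-blind. Neither is open-label.

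**Illustration of size** (hypothetical data). Suppose one of the 4 planned vehicle subjects has an abnormal reading only at such a follow-up ECG. Rule B shows 1/4 = 25% in the vehicle column. Rule A shows 0/4 there and adds one subject to open-label: 1/12 = 8.3% if all 12 enter, or 1/6 = 16.7% if six do.

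**The case against.** The strongest reply is that the sentence has a sensible purpose. A final post-treatment visit falls after dosing has ended, so someone must say which table it joins. Visit 16 is at Day 59 for non-continuers and Day 393 for the rest, and sorting by entry gets both right. The clause opens with a qualifier, and the sentence before it already splits data by period of collection. Section 4 also defers detail to a data handling and programming specifications document, not supplied, which may contain a date rule. That reading fits the current schedule, and timelines 1 to 3 bear it out. It does not remove the gap: the parenthesis as written has no date condition, and a date rule elsewhere would contradict it.

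A reader might infer something stronger: that every subject with an administrative gap has a post-double-blind ECG counted as open-label. The documents do not support that. The Day 29 ECG stays double-blind, the early Visit 16 is meant for subjects who decline or are ineligible, and late entry lists no ECG. A gap without a follow-up ECG before entry misfiles nothing.

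It can also be said that a date rule has a cost: it could put an ECG taken long after the last application into the double-blind table and lengthen the observation window for some subjects. This stands in part. SAP 4.4.4 already places non-entrants' Day 59 ECGs in double-blind, so the principle is not new, but late readings should be marked.

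Finally, the Visit 5 and Visit 7 ECGs remain in the double-blind table whichever rule is used, so the on-treatment comparison is intact.

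**Conclusion.** The point holds as a conditional one. SAP 4.4.4 lacks a date condition, and a follow-up ECG taken before the first open-label application would be classed as open-label, contrary to SAP Section 4 and out of step with the date-based rule in 4.4.1.

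It rests on one assumption: that at least one subject had a follow-up ECG after the double-blind period and before starting open-label drug. The amendment history and the leftover Visit 8 text in Protocol 7.5 make this plausible; neither proves it, and the number of such subjects is not given.

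The size is small. At most one ECG per affected subject moves under the schedule examined. It alters the open-label category only if it is worse than the readings at Visits 9, 13 and 16, and the double-blind category only if it is worse than those at Visits 5 and 7. The table is descriptive, covers about 12 subjects and carries no test or decision rule.

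**What to change.** Replace the parenthesis in SAP 4.4.4 with a date rule:

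- ECGs taken before the first open-label application are never counted as open-label. Post-baseline ones, including follow-up visits, go to the double-blind summary, as non-entrants' follow-up ECGs already do.
- Those taken more than 30 days after the last double-blind application are flagged as off-treatment, in line with 4.4.1. The flag should apply to entrants and non-entrants alike; a nominal Day 59 ECG, 31 days after Day 28, would carry it.
- ECGs on or after the first open-label application go to the open-label summary.

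Check that the data handling and programming specifications say the same. The cost is a short SAP edit, one date comparison in the program and one flag. The small downside is that some gap subjects get a longer double-blind observation window than subjects who entered directly; the flag makes this visible. Subjects on timelines 1 to 3 keep the same table allocation.

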#### **4.4.5 Laboratory Evaluations**

Shift tables showing changes in relationship to the normal reference range grade from baseline to the "worst" relationship recorded post-baseline are tabulated. In the event a patient had both "low" and "high" post-baseline values the patient will be counted under both "low" and "high". As such the percentages of the cells in the shift table may add to more than 100%.

Chemistry and Hematology parameters are summarized using descriptive statistics for each visit. Both actual values and changes from baseline are summarized.

The number and percentage of patients meeting criteria for hepatobiliary abnormalities and for potential renal impairment are provided for Double-Blind ATI-50002, Double-Blind Placebo, Open-Label ATI-50002 and Total ATI-50002 (Double-Blind + Open-Label).

### **4.5 Pharmacokinetic Analyses**

Levels of ATI-50002 in the scalp biopsy is summarized for V3 (Day 2) and V7 (Day 29) using simple descriptive statistics. Only values that are quantifiable are included in the mean, SD, etc.; however, a separate summary of the number and percentage of patients with value that were BLQ (below limit of quantification) is provided.

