Study Design: During the double-blind period, this Phase 2, multicenter, randomized study is designed to evaluate the safety, tolerability, pharmacokinetics and pharmacodynamics of ATI-50002 Topical Solution in subjects with AU and AT. Subjects will be required to have a clinical diagnosis of stable, clinically typical, AU or AT for a duration of at least 6 months up to and including seven years. In the double-blind phase, a total of approximately 12 subjects will be randomized to a 2:1 ratio: 
 • ATI-50002 Topical Solution, 0.46%, BID for 28 days (8 subjects) • Vehicle Solution BID for 28 days (4 subjects) During the screening period, subjects will be assessed for eligibility into the study. Subjects who meet all the entry criteria will be randomized to ATI-50002 Topical Solution, 0.46% or Vehicle Topical Solution and will apply a minimum of 1.5 mLs up to a maximum of 4 mLs of study medication to the entire scalp twice-a-day (BID) for 28 days (except for Day 1 and Day 28 when study medication will only be applied once a day). For the first 6 subjects enrolled in the study, blood samples for concentrations of ATI-50002 will be collected on Day 1 (Visit 2) and Day 28 (Visit 6) at pre-dose and 1, 2, 4, 8 hours post dose and on Day 2 (Visit 3) and Day 29 (Visit 7) at 24 hours post-dose. Blood samples for immunology will be collected on Day 1 (Visit 2) before study medication application and on Day 29 (Visit 7), 24 hours after study medication application on Day 28 (Visit 6). A 4-mm punch biopsy of the scalp will be obtained to determine the concentration of ATI-50002 in the scalp skin on Day 2 (Visit 3) and on Day 29 (Visit 7) 24 hours after study medication application on Day 1 (Visit 2) and on Day 28 (Visit 6). A 4-mm punch biopsy will be obtained to determine histology and immunology, prior to study medication application on Day 1 (Visit 2) and on Day 29 (Visit 7), 24 hours after study medication application on Day 28 (Visit 6). Safety and tolerability will be evaluated	

at each study visit by assessment of adverse events and vital signs, and at select visits, ECGs and clinical laboratory tests will be completed.

Open-Label Extension:

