### 4.1 Study Populations, Disposition, Baseline Characteristics, Medical History Concomitant Medications, Exposure and Protocol Violations

#### 4.1.1 Analysis Populations

The efficacy and safety populations will be defined as follows:

- As-Treated population (AS): This population includes all patients with at least one application of study treatment. This population will be used for pharmacodynamics and safety analyses. All analyses using this population will be based on the treatment actually received.
- Blood Pharmacokinetic (PK1) population: This population includes patients participating in the PK assessment who had evaluable blood plasma measurements with no significant protocol deviations that may impact the data.
- Scalp Pharmacokinetic (PK2) population: This population includes patients participating in the PK assessment who had evaluable scalp biopsy measurements with no significant protocol deviations that may impact the data.
- Pharmacodynamic (PD) population: This population includes all randomized patients who had at least 1 evaluable pharmacodynamic measurement.

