#### **4.1.6 Exposure to Study Medication and Study Medication Administration**

Exposure will be summarized and listed for the AS population with separate summaries from double-blind and open-label periods. Additionally, the combined exposure to ATI-50002 from the double-blind and open-label periods will be tabulated.

The duration of treatment, total weight, total volume, and average volume per application will be summarized using descriptive statistics (n, mean, SD, median, minimum and maximum).

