## **4.2 Pharmacokinetic Endpoints**

### **4.2.1 Blood Levels of ATI-50002**

The blood levels of ATI-5002 will be listed only.

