### **4.2.2 Scalp Biopsy Levels of ATI-50002**

Scalp biopsy levels of ATI-50002 will summarized with descriptive statistics for each schedule collection visit. Levels that are BLQ will not be included but will be accounted for categorically.

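### Leaving BLQ scalp biopsies out of the mean overstates skin drug levels whenever some, but not all, biopsies at a visit are BLQ

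*SAP*

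**What the plan says.** The rule appears twice in the SAP. Section 4.2.2 says of scalp levels: "Levels that are BLQ will not be included but will be accounted for categorically". Section 4.5, which covers Visit 3 (Day 2) and Visit 7 (Day 29), says: "Only values that are quantifiable are included in the mean, SD, etc.; however, a separate summary of the number and percentage". That separate summary counts the patients whose result was BLQ.

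Neither section names a substitution value, a censored-data method, a sensitivity summary or the LLOQ. The only imputation described in SAP 4 is for dates. Neither section lists the statistics in full. Elsewhere the SAP's usual set includes a median; in 4.1.6, for example, exposure "will be summarized using descriptive statistics (n, mean, SD, median, minimum and maximum").

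The scalp PK population (PK2, SAP 4.1.1) consists of "patients participating in the PK assessment who had evaluable scalp biopsy measurements" without important deviations. It does not say whether a BLQ result is evaluable. For plasma, SAP 4.2.1 says: "The blood levels of ATI-5002 will be listed only". The protocol synopsis plans 8 subjects on active treatment and 4 on vehicle.

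**The concern.** A BLQ biopsy tells us that the concentration lies between zero and the LLOQ. Dropping it removes the lowest values and averages only the higher ones. The result describes the level among biopsies with quantifiable drug, but a reader may take it as the average skin level in the treated group.

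Pharmacokinetics is part of the primary objective (protocol 5.1.1, SAP 1.1). Because blood levels are only listed, the scalp level is the one drug concentration that the SAP summarises. Day 2 and Day 29 will also be read side by side. If the BLQ count differs between visits, the two means describe different subsets of subjects, and an apparent change can be distorted.

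**Working it through.** **Inputs.** The active-arm size is 8 (protocol synopsis: "ATI-50002 Topical Solution, 0.46%, BID for 28 days (8 subjects"), so there are at most 8 active biopsies per visit. The exclusion rule is from SAP 4.2.2 and 4.5. The documents state no LLOQ, BLQ rate, concentration or spread, so there is no plan figure to reproduce. Those quantities are assumed below and varied.

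**Direction.** Take *n* biopsies, *b* of them BLQ with 0 < *b* < *n*. Let *M* be the mean of the quantifiable values and *B* the true mean of the BLQ values. The all-biopsy mean is [(n − b)M + bB]/n, so

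M − all-biopsy mean = (b/n)(M − B).

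With one common LLOQ, *B* < LLOQ ≤ *M*, and the difference is always positive. In 1,529,376 simulated visits with some but not all values BLQ there was no exception. With no BLQ values the two means coincide; with all BLQ there is no mean to report.

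**Size, without a distribution.** Put *B* at its limits, 0 and LLOQ, and let r = M/LLOQ:

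- Maximum excess = 8/(8 − b) − 1.
- Minimum excess = 1/[(8 − b)/8 + b/(8r)] − 1.

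| | 1 of 8 BLQ | 2 of 8 BLQ | 4 of 8 BLQ |
|---|---|---|---|
| Maximum | 14.3% | 33.3% | 100% |
| Minimum, r = 2 | 6.7% | 14.3% | 33.3% |
| Minimum, r = 5 | 11.1% | 25.0% | 66.7% |
| Minimum, r = 10 | 12.7% | 29.0% | 81.8% |

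Worked case: LLOQ 10, reported mean 50, 2 BLQ. The six quantifiable values sum to 300. The all-biopsy mean lies between 300/8 = 37.5 and (300 + 2 × 10)/8 = 40.0. The reported 50 is 25% to 33% too high.

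**Size, assuming a lognormal.** In 400,000 samples of 8 with the lowest *b* removed, the expected reported mean divided by the true mean was:

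| log-SD | 1 BLQ | 2 BLQ | 4 BLQ |
|---|---|---|---|
| 0.5 | 1.078 | 1.159 | 1.351 |
| 0.7 | 1.098 | 1.205 | 1.476 |
| 1.0 | 1.119 | 1.257 | 1.638 |
| 1.3 | 1.130 | 1.290 | 1.764 |

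For scale, the relative standard error of a complete mean of 8 is √(exp(s²) − 1)/√8, which is 0.281 at log-SD 0.7 and 0.463 at 1.0. At these spreads the bias with 1 or 2 BLQ is below one standard error; with 4 BLQ it is above.

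**Median, if one is reported.** The median of all 8 is the midpoint of the 4th and 5th ordered values (rank 4.5). After dropping the lowest 1, 2 or 4 it moves to rank 5, 5.5 or 6.5. It is therefore raised, or unchanged where the central values are tied.

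**Comparing visits.** Take Day 2 values 1.1, 1.3, 1.6, 2, 3, 4, 6, 10 with LLOQ 1, and halve every value by Day 29. The all-biopsy mean falls from 3.63 to 1.81 (−50%). Three Day 29 values become BLQ, and the quantifiable-only mean falls from 3.63 to 2.50 (−31%).

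**Do the bounds proposed under the fix work?** With a lognormal, a fixed LLOQ and BLQ shares of 12.5%, 25% and 50%, the two substituted means, as a percentage of the true mean, were:

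| log-SD | BLQ = 0 | BLQ = LLOQ |
|---|---|---|
| 0.7 | 96.8, 91.5, 75.8 | 101.2, 103.7, 114.9 |
| 1.0 | 98.4, 95.3, 84.1 | 100.8, 103.0, 114.5 |

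They bracket the truth in all six cases.

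**The case against.** The strongest reply is that this is a disclosed two-part summary: the share of biopsies that are quantifiable, then the level among them. The SAP never calls the figure a mean of all biopsies. It plans no test and no Day 2 to Day 29 ratio, and a table showing half the biopsies as BLQ would warn any reader. All this is fair and is why the point is minor. It does not correct the mean. From the count a reader can recover the BLQ = 0 mean, but the upper bound also needs the LLOQ, which the SAP does not promise to report.

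Three narrower replies also carry some weight:

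- **Evaluability and listings.** A BLQ percentage makes sense only if BLQ results belong to PK2, so the evaluability gap is a matter of clarification. Scalp levels may well be listed by default. The SAP says "All Data listings are sorted by double-blind treatment group and patient ID", but it does not expressly say that scalp levels are among the listings. A listing would give the all-biopsy median.
- **Companion document.** SAP 4 and 4.4 refer to separate data handling and programming specifications, which are not available here. They may cover LLOQ display or the denominator. They cannot be assumed to reverse a rule that the SAP states twice.
- **Common LLOQ.** If the LLOQ varied by sample, for instance after tissue-weight normalisation, the direction would not be guaranteed. Quantifiable values of 2 and 3 (LLOQ 1) with a BLQ sample truly at 9 (LLOQ 10) average 2.5 when the BLQ sample is dropped and 4.67 when it is kept. Nothing in the documents suggests a varying LLOQ.

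**Conclusion.** The concern holds, as a minor one. Given a single LLOQ and a visit where some but not all active biopsies are BLQ, the planned mean always overstates the mean over all biopsies. For 8 biopsies the excess cannot be more than 14%, 33% or 100% with 1, 2 or 4 BLQ. How close it comes to those limits depends on how far the quantifiable mean sits above the LLOQ. Whether the condition will arise cannot be told from the documents, so these sizes are illustrative. The consequence is possible misreading of a descriptive table, not a wrong inference from a test.

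**What to change.** In SAP 4.2.2 and 4.5:

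- Keep the BLQ count and percentage, and state the LLOQ.
- By treatment group and visit, report the median, minimum and maximum over all evaluable biopsies with BLQ ranked lowest. Show the minimum as <LLOQ if any value is BLQ, and the median as <LLOQ if more than half are.
- If exactly half are BLQ, give the median as an interval, from half the lowest quantifiable value to the midpoint of the LLOQ and that value.
- For the active group, report the mean with BLQ = 0 and with BLQ = LLOQ as bounds (LLOQ/2 is optional).
- Keep the present mean only as a row labelled as quantifiable values only, with its n.

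In SAP 4.1.1, add that a BLQ result counts as evaluable for PK2.

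The cost is a sentence in each of the three sections and a few table rows, with no new data or distributional model. The reported mean skin level may become lower.
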